4.4.2.1 Hypothesis Testing for Secondary Efficacy Endpoints

A hierarchical testing procedure will be employed to control the overall Type I error rate of the analysis of the primary and secondary endpoints. For each secondary endpoint specified in the hierarchy, the closed testing procedure described in Section 4.4.1 will be applied for all endpoints up to the point where a secondary endpoint fails to reject a null hypothesis at either step in the procedure for a given dose arm. Results of all analyses performed after the incidence of a result that fails to reach statistical significance for that dose arm will be considered exploratory.

Hypothesis testing of the secondary endpoints will be performed using the following pre-specified hierarchy:

1. 6MWD
2. 4-stair climb velocity
3. Stand from supine velocity
4. 10-meter walk/run velocity

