| Secondary   | 
Following testing of the primary endpoint, the key secondary endpoints will be analyzed using a hierarchical testing procedure in order to maintain the overall type I error rate at 0.05. This procedure will be specified in the Statistical Analysis Plan prior to database lock.
 
Most secondary endpoints will be tested using a MMRM that is similar in structure to the primary analysis. Proximal lower extremity flexor strength will be tested using a MANOVA of the 2 component variables: knee extension and knee flexion.
 
If a dose fails to reach significance against placebo in any stage of the testing hierarchy, any further tests will be considered as exploratory.
   |
| Exploratory | Will be described in the Statistical Analysis Plan finalized before database lock   |

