4.4 EFFICACY ANALYSIS AT END OF DOUBLE-BLIND TREATMENT

4.4.1 Primary Efficacy Endpoint

The primary analysis, on the change from baseline in NSAA total score after 48 weeks of double-blind treatment, will be conducted using a Mixed Model Repeated Measures (MMRM) analysis with treatment, visit, treatment-by-visit interaction, age stratum, and CS stratum entered into the model as fixed effects, and subject entered as a random effect. The baseline value of the NSAA total score will be entered into the model as a covariate. The modified ITT population will be the analysis population for the primary

efficacy analysis. An unstructured correlation within subject will be used. In the case that this does not converge, a compound symmetry structure will be used.

For each RO7239361 dose group, the null hypothesis of no treatment difference between the dose group and placebo will be tested using the estimates from this MMRM model at the end of the 48-week double-blind treatment period. In order to control the overall Type I error rate for the analysis of the primary endpoint, the following testing procedure (based on the closed testing principle) will be implemented:

1. Comparison of the pooled RO7239361 doses to placebo (intersection hypothesis) at a 2-sided α -level of 0.05 is performed.
2. If the result from the previous step is significant, then a comparison of the RO7239361 high dose (35/50 mg) to placebo and a comparison of the low dose (7.5/15 mg) to placebo will both be performed at a 2-sided α -level of 0.05.

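### The SAP's secondary hierarchy stops dose by dose at full alpha, so it does not control the overall type I error rate as stated

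*SAP*

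**What the plan says.** SAP 4.4.2.1 gives the purpose: "A hierarchical testing procedure will be employed to control the overall Type I error rate of the analysis of the primary and secondary endpoints". Protocol 10.3.1 sets the level, "in order to maintain the overall type I error rate at 0.05", and leaves the details to the SAP.

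The test repeated at each endpoint is the one in SAP 4.4.1. Step 1 is "Comparison of the pooled RO7239361 doses to placebo (intersection hypothesis) at a 2-sided" level of 0.05. Step 2, reached only if step 1 succeeds, tests each dose separately against placebo, again at two-sided 0.05.

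SAP 4.4.2.1 then carries this through six ordered secondaries: 6MWD, 4-stair climb velocity, stand from supine velocity, 10-metre walk/run velocity, CGI-C and ActiMyo stride velocity. Testing continues until an endpoint "fails to reject a null hypothesis at either step in the procedure for a given dose arm". The consequence is also tied to the dose: "Results of all analyses performed after the incidence of a result that fails to reach statistical significance for that dose arm will be considered exploratory".

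Protocol 10.3.1 has a related sentence without that restriction on the consequence: "If a dose fails to reach significance against placebo in any stage of the testing hierarchy, any further tests will be considered as exploratory".

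**The concern.** The pooled comparison is the intersection test for two doses on one endpoint. It closes the testing within an endpoint but not across the family of seven endpoints by two doses. Nothing tests, for example, the joint hypothesis that the low dose is null on NSAA and the high dose is null on 6MWD.

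If the low dose is first null at one endpoint and the high dose is first null at another, each of those true nulls gets its own 0.05 test. A dose that has already failed also stays in the pooled comparison for the surviving dose. A real effect of the failed dose on a later endpoint can therefore hold the gate open for a surviving dose that has no effect there.

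The claims at stake are the dose-specific secondary ones, such as 6MWD or stair climb. They would be reported as confirmatory under a 5% guarantee that the procedure does not provide.

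**Working it through.** **Inputs.** SAP 2.3: 53 per arm, difference 2.5 points, SD 4.4, 5% discontinuation. SAP 4.4.1: two-sided 0.05 at each step. SAP 4.4.2.1: NSAA, then six ordered secondaries. Neither document gives the correlation between endpoints, so it is assumed and varied.

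**1. The plan's own figures.** Evaluable per arm: 53 × 0.95 = 50.35, taken as 50.
- Single dose: SE = 4.4 × √(2/50) = 0.880; 2.5/0.880 = 2.841; power = Φ(2.841 − 1.960) = 81.1% (80.3% with the t distribution).
- Pooled: SE = 4.4 × √(1/50 + 1/100) = 0.762; 2.5/0.762 = 3.280; power = Φ(1.320) = 90.7%.

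The stated 80% and 90% reproduce. The planned effect is 2.5/4.4 = 0.568 SD.

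**2. The guaranteed bound.** Within one dose's chain, any false rejection requires that dose's first true null to be rejected, and that null is tested at 0.05.
- First nulls on the same endpoint: the pooled null there is also true, so the error is at most 0.05.
- First nulls on different endpoints: at most 0.05 + 0.05 = 0.10; under independence 1 − 0.95² = 0.0975.

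**3. What the gate does when one dose works.** Let one dose have effect d SD on an endpoint and the other none. The pooled z has mean (d/2)/√(1/50 + 1/100) = (d/2)/0.1732, and its correlation with the null dose's z is √(0.03/0.04) = 0.866.
- d = 0.568: mean 0.284/0.1732 = 1.64. If the null dose's z is +1.96, the expected pooled z is 1.64 + 0.866 × 1.96 = 3.34 and the gate opens. If it is −1.96, the expected pooled z is 1.64 − 1.70 = −0.06 and the gate stays shut.
- d = 1.5: mean 0.75/0.1732 = 4.33. Even at −1.96 the expected pooled z is 4.33 − 1.70 = 2.63, so both directions pass.

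At the planned size, then, the gate blocks false harm but lets false benefit through almost unhindered. With large effects it blocks neither.

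**4. Simulation, three ordered endpoints** (1,000,000 trials, 50 per arm, correlation 0.3). The high dose is effective on the first endpoint only; the low dose is null on the first and effective on the second and third. Each cell is two-sided family-wise error / false benefit.

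| True effect (SD) | NSAA points (× 4.4) | SAP rule | Advance only if both reject |
|---|---|---|---|
| 0.568 | 2.5 | 3.9% / 3.9% | 2.5% / 2.5% |
| 1.0 | 4.4 | 4.8% / 4.7% | 2.6% / 2.5% |
| 1.1 | 4.8 | 5.1% / 4.8% | 2.7% / 2.5% |
| 1.5 | 6.6 | 8.4% / 4.9% | 4.3% / 2.5% |
| 2.0 | 8.8 | 9.7% / 4.9% | 5.0% / 2.5% |

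A second pattern has both doses effective on the first endpoint, only the high dose on the second and only the low dose on the third. Over both patterns and correlations 0.3–0.5, the SAP rule gives 8.3–8.4% at 1.5 SD and 9.5–9.7% at 2 SD. False benefit is 3.7–4.2% at the planned 0.568 SD.

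**5. Simulation, NSAA plus all six secondaries** (400,000 trials; correlation 0, 0.3, 0.5 and 0.8; ranges are over correlation).

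| True pattern | SAP, two-sided | SAP, false benefit | Both must reject, two-sided |
|---|---|---|---|
| Both doses null throughout | 4.4% | 2.2% | 4.3–4.4% |
| Both effective on NSAA (large), null from 6MWD on | 4.4% | 2.2% | 4.4% |
| High effective on NSAA only, planned size; low null throughout | 3.4–3.6% | 3.0–3.5% | 2.5% |
| Same, large effect | 6.9–7.5% | 3.4–3.8% | 5.0% |
| High on NSAA and 6MWD, low on NSAA only, planned size | 2.8–3.5% | 2.4–3.5% | 1.8–2.5% |
| Same, large effects | 7.1–7.5% | 3.5–3.9% | 4.93–5.05% |
| Low null on NSAA but effective from 6MWD on; high the reverse; large | 9.3–9.7% | 4.7–4.9% | 5.0% |
| Both on NSAA; low null on 6MWD; high null and low effective on 4SCV; large | 9.2–9.7% | 4.6–5.0% | 5.0% |

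The simulation standard error at 5% is √(0.05 × 0.95/400,000), or 0.03 percentage points. False benefit under the both-must-reject rule was at most 2.6%. The part above 2.5% comes from a false benefit that follows a false rejection in the harm direction.

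**The case against.** **The text has another reading.** The dose phrase in the SAP sentence could describe only which result failed, so that everything later becomes exploratory for both doses. The protocol sentence can be read that way too, and on that reading the error is controlled. This does not hold up well. The SAP attaches the dose qualifier twice, in the stopping rule and in its consequence, and stopping both doses would leave it without effect. The protocol hands the procedure to the SAP. At the least, the two sentences need aligning.

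**The chains are not fully separate.** True. They share the pooled gate, which holds the error at 4.4% when the first nulls coincide. As a gate it can only remove rejections, so keeping a failed dose in it does not itself create error; it only makes the gate a weaker safeguard than it looks.

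**The two-sided excess needs implausible effects.** This stands as a limit on size. It appears only above about 1.1 SD, or 4.8 NSAA points against a planned 2.5, and the 8–10% figures need 6.6 to 8.8 points. The worst patterns also have the two doses acting on different endpoints, while Protocol 3.1.1 expects similar serum myostatin suppression from both, though it allows that tissue effects may differ. In the dose-ordered patterns the large-effect figure is about 7–7.5%.

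**The 2.5% false-benefit limit is derived.** Correct: neither document states it. It is the half of a two-sided 5% that supports an efficacy claim, and it is the only measure that shows an excess at planned effects.

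**Conclusion.** The point holds. The rule controls the error when both doses are null from the same endpoint onward, but not for every pattern of true effects, which is what the SAP's statement requires. The guaranteed bound is 10%, and the highest simulated value is about 9.7%.

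At the planned effect size, the two-sided error stayed below 5% in every pattern tabulated above. False benefit there was 3.7–4.2% where the doses act on different endpoints, and 2.4–3.5% in the simpler staggered patterns.

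These sizes assume 50 evaluable per arm, normally distributed and fully observed endpoints, and assumed correlations. CGI-C is in fact categorical, and stride velocity is measured only in a subset. The bound in step 2 depends on none of these assumptions. Type I error control for the primary endpoint on its own is not in question.

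**What to change.** Replace the per-dose stopping sentence in SAP 4.4.2.1 with a common chain: the next endpoint is tested formally only if both doses were rejected at the current one; otherwise all later tests, for both doses, are exploratory. Bring the wording of Protocol 10.3.1 into line.

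This controls the error by a direct argument. Take the first endpoint at which either dose is truly null. No later endpoint opens unless both doses are rejected there, so any later error implies an error at that endpoint. The error there is at most 0.05: by the single-dose test if one dose is null, and by the pooled test if both are.

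The cost is SAP wording only. Every test stays at 0.05, and the primary analysis, sample size and data collection are unchanged. The downside is that one dose loses its formal secondary claims when the other fails.

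If dose-specific chains are wanted, a graphical procedure could start each dose at 0.025 and pass alpha on when a chain completes. That is a real trade-off, because it also lowers the starting level for NSAA. With a plain split at 0.025, single-dose power falls from 81.1% to 72.6%, and 80% power would need 59 evaluable or 63 randomized per arm (63 × 3 = 189 in total). The remaining option is to withdraw the overall-control statement for the secondary endpoints.

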5. CGI-C
6. 95% stride velocity from ActiMyo.

4.4.3 Exploratory Efficacy Endpoints

Analysis of the continuous exploratory efficacy endpoints will be performed (comparing the change from baseline to week 48 between each RO7239361 dose group and the placebo group) using MMRM models similar in structure to that used for the primary and secondary efficacy endpoints. No formal hypothesis testing will be performed for the exploratory efficacy endpoints.

The distribution of CaGI-C responses at week 48 will be summarized using descriptive statistics, as described above.

4.4.4 Sensitivity Analyses

In order to assess the impact of the presence of missing data on the results of the primary and secondary efficacy analyses using an MMRM analysis, additional analyses may be performed using methodologies such as multiple imputation methods with pattern mixture models. Final specifications of the methods used to handle missing data in these additional analyses will be finalized prior to the primary efficacy analysis, and will be determined based on characteristics including the proportion of subjects discontinuing treatment, and the reasons for discontinuation. The rate of missing data is expected, however, to be low.

For selected continuous efficacy endpoints, additional analyses may be performed using:

- an analysis of covariance (ANCOVA) model on the mITT data set using the observed change from baseline at week 48 as the dependent variable, treatment, age stratum, and CS stratum as fixed effects, and baseline value as a covariate.
- ANCOVA (at week 48) and MMRM models on the mITT data set with missing data imputed using multiple imputations with pattern mixture models
- an MMRM analysis using the per-protocol analysis population.

In this population, the treatment discontinuation and study discontinuation rates during the 48-week double-blind treatment period are expected to be low (as reflected in the 5% assumed treatment discontinuation rate incorporated into the sample size calculation).

This expectation is based on:

- the low treatment discontinuation rate, and overall safety and tolerability profile of RO7239361, to date from the ongoing WN40226 study
- the treatment discontinuation rates in the phase III 48-week double-blind studies in with ataluren and drisapersen DMD ambulatory patients
- the relatively short (compared to other competing clinical trials in DMD patients) double-blind treatment duration of 48 weeks
- the inclusion of a safety follow up visit (which also includes an NSAA assessment) for those subjects who discontinue, which should reduce the number of missing assessments of the primary efficacy endpoint.

It is not expected that there will be other frequently occurring intercurrent events (i.e., introduction of rescue medications) that will materially affect the efficacy assessments or that could motivate a decision to exclude values recorded after such an event.

Based on these assumptions, it is anticipated that the results from sensitivity analyses will not differ appreciably from the protocol-specified primary efficacy analysis. Therefore, a treatment policy estimand calculated using the results from an MMRM analysis of the data from the modified ITT population described above (all subjects randomized, with a baseline and post-baseline efficacy assessment) is proposed as appropriate for the primary evaluation of the efficacy of RO7239361 in this study.

4.4.4.1 Additional Analyses of the Primary Endpoint

Additional analyses of the NSAA scores at week 48 may be performed using the following:

- The proportion of subjects with a decline of 3 or more points in the NSAA total score
- Change from baseline in linearized NSAA total score
- Number of NSAA items transitioning from a non-zero baseline score to a zero score at week 48
- Number of NSAA items with small improvement (one-point improvement from baseline) or stability (no change from baseline) at week 48

- Proportion of subjects with loss of ambulation, based on ability to walk recorded in NSAA
- Cumulative distribution function of the change from baseline in NSAA total score
- Cumulative distribution function of the number of items with improvement from baseline
- Cumulative distribution function of the number of items with deterioration from baseline.

4.4.5 Subgroup Analyses

Exploratory subgroup analyses may examine the impact of genetic variations in the dystrophin gene or in genes suspected to impact DMD disease expression (including but not limited to LTBP4, SPP1) and their impact on target engagement, pharmacodynamic (PD), and selected functional endpoints.

Subgroup analyses may also be performed based on the randomization strata (age group and baseline CS regimen) and subgroups defined based on baseline levels of selected functional and imaging endpoints.

4.5 EFFICACY ANALYSIS OF OPEN-LABEL DATA

For the functional efficacy endpoints, additional analyses may be performed on subjects continuously treated with RO7239361 for 96 weeks (48 weeks of double-blind treatment followed by 48 weeks of open-label treatment). These data will be compared to pre-specified external control data from research cohorts such as disease registries and placebo arms from previous trials after evaluation of data quality and comparability of subjects in these data sources with subjects in the WN40227 trial. Specifications of this analysis will be documented in a separate statistical analysis plan, and will be finalized prior to the analysis.

4.6 PHARMACOKINETIC AND PHARMACODYNAMIC ANALYSES

Pharmacokinetic and PK/PD analyses will be summarized in an analysis plan and report separate from the CSR.

4.7 SAFETY ANALYSES

Adverse events, including abnormal laboratory findings, will be defined using the National Cancer Institute (NCI) Common Terminology for Adverse Events (CTCAE, version 5), and will be coded according to the most recent Medical Dictionary for Regulatory Activities (MedDRA) version. Adverse events will be summarized according to the MedDRA coded Preferred Terms (PT) by System Organ Class (SOC). Previous and concomitant medications will be coded using the WHO Drug Dictionary version.

The evaluation of safety is based on clinical AEs, vital signs, echocardiogram, ECG results, and clinical laboratory results reported during the study. Cardiac MRI measures

may also be included in the safety assessment. Safety analyses will be performed using the treated subjects. For AEs, all enrolled subjects will be listed.

Safety analysis data displays will be generated for the following:

- the double-blind treatment period, with baseline defined as the last visit prior to the start of the double-blind treatment period
- all active treatment during both the double-blind and open-label treatment periods (excluding data from the placebo subjects during the double-blind period); for this analysis, baseline will be defined as the last visit prior to the start of active treatment for each subject (i.e., the start of double-blind treatment period for those subjects randomized to active treatment from study start, or the start of the open-label treatment period for those subjects randomized to double-blind placebo and who are switching to active treatment at the start of the OLE).

4.7.1 Exposure of Study Medication

Duration of exposure will be summarized descriptively. Study drug administration, randomization schedule and batch numbers will be documented as per subject listings.

Any non-study medications taken by subjects, any conducted non-study medical treatment procedures, and any utilized non-study diagnostic procedures will be summarized separately.

4.7.1.1 Study Therapy Compliance

As study drug will be administered weekly, a dose will be considered to be taken in compliance if it is either the first injection or is taken within 5-9 days of the previous injection. Compliance rate is defined as the number of doses taken in compliance, divided by the number of expected doses.

A subject will be considered compliant if $\geq 80\%$ and $\leq 110\%$ of doses are taken in compliance. The number and percentage of compliant subjects will be presented.

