### Study Treatment:

Each participant will be administered weekly, SC doses of RO7239361 (previously, BMS-986089) or placebo for 48 weeks in a randomized, double-blind design. Participants who complete the 48-week double-blind phase are eligible to receive OL RO7239361 (active treatment) as part of an OL extension phase of this study. The OL extension phase will last up to 192 weeks or until RO7239361 is commercially available in the subject's country, per local regulations, or the study is terminated by the Sponsor, whichever comes first. Please refer to [Section 7.8](#) for details regarding treatment after the end of study. Doses in the OL extension phase may be adjusted based on emerging data.

| Study Drug                 |                            |           |
|----------------------------|----------------------------|-----------|
| Medication                 | Potency                    | IP/Non-IP |
| RO7239361 7.5 mg dose      | 10.7 mg/mL (0.7mL/syringe) | IP        |
| RO7239361 15 mg dose       | 21.4 mg/mL (0.7mL/syringe) | IP        |
| RO7239361 35 mg dose       | 50 mg/mL (0.7mL/syringe)   | IP        |
| RO7239361 50 mg dose       | 71.4 mg/mL (0.7mL/syringe) | IP        |
| RO7239361 matching placebo | 0 mg/mL (0.7mL/syringe)    | IP        |

Other medications used as support medication for preventative, diagnostic, or therapeutic reasons, as components of the standard of care for a given diagnosis, may be considered as non-investigational products. In this study, corticosteroids are considered *a* non-investigational product and will not be provided by the sponsor.

Study drug preparation and administration instructions will be provided in a separate manual.

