**Table 2-2: On Treatment Procedural Outline, Double-Blind Phase**

| Procedure                        | D1 a | D8
±1 day
(Wk 1) | D15
±1 day
(Wk 2) | D29
±1 day
(Wk 4) | Wk 6
±3 days | Wk 12
±3 days | Wk 18
±3 days | Wk 24
±3 days | Wk 30
±3 days | Wk 36
±3 days | Wk 42
±3 days | Wk 48 or
early D/C
±3 days | Notes  |
|----------------------------------|-----------------|------------------------|-------------------------|-------------------------|-----------------|------------------|------------------|------------------|------------------|------------------|------------------|----------------------------------|--|
| Weekly Study Drug Administration | X               | X                      | X                       |                         |                 |                  |                  |                  |                  |                  |                  |                                  | RO7239361 (BMS-986089) or placebo will be administered every week (every 7 ± 2 days, unless otherwise stated). Parents/caregivers will be trained to administer SC injections. Parents/caregivers can administer the injection starting at Day 22. Parents/caregivers will be dispensed approximately 6 week supply of prefilled syringes (RO7239361 or placebo) for weekly study drug administration to the participant. On site study visit days, participants should be dosed in clinic, after PK, myostatin and immunogenicity sampling. |

a Day 1 must occur within 42 days of the screening visit. Some Day 1 procedures (ECG, TFTs, 6MWD, NSAA, PFTs, Upper and Lower Extremity Myometry, Grip and Pinch Strength, right ankle range of motion, PUL, PODCI, HUI-3 and PedsQL Family Impact Module) may be completed on Day -1 to accommodate subject's schedule.

b Falls will be reported as an adverse event if worsening occurs (e.g., more frequent falls) compared with pre-treatment.

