3. STUDY CONDUCT

Significant protocol deviations identified by site monitor or site manager will be provided by the protocol manager who is responsible for study management. The following protocol deviations will be defined as relevant protocol deviations (RPDs) and listed. It should be noted, for the RPDs that occur after treatment initiation (RPDs #5 #6 #7), subjects are still under consideration and included in the per-protocol analysis until the time point that the protocol deviations started.

1. DMD not confirmed by medical history (e.g., onset of clinical signs or symptoms before 5 years of age together with an elevated serum creatine kinase level) and by genotyping;
2. Subject not male or not ≥ 6 to < 12 years of age at randomization;
3. Subject not on CS for ≥ 6 months (182 days) prior to randomization;
4. No established 4 stair climb ≤ 8 seconds prior to randomization;
5. Treatment with prohibited medication (listed in Section 7.7.1 of Protocol) for ≥ 7 days at any time during the study or during the 3-month period prior to initiation of study treatment;
6. Dosing that deviates $\geq 20\%$ of the intended dose for > 2 weeks (> 2 doses). This addresses subjects getting the correct treatment, but not the correct dose
7. Incorrect treatment received for ≥ 2 weeks (> 2 doses). This addresses incorrect allocation of subject to active or control and missed doses.

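### The SAP compliance rule counts an isolated missed dose twice, so its 80% cut depends on the pattern of misses as well as on how many doses were taken

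*SAP*

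**What the plan says.** SAP 4.7.1.1 (Study Therapy Compliance) sets the rule in three parts.

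- Which doses count: "a dose will be considered to be taken in compliance if it is either the first injection or is taken within 5-9 days" of the injection before it.
- The rate: "Compliance rate is defined as the number of doses taken in compliance, divided by the number of expected doses".
- The label: a boy is compliant if the rate is at least 80% and at most 110%. The output is a table: "The number and percentage of compliant subjects will be presented".

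The 5-9 day window mirrors Protocol Table 2-2, where study drug "will be administered every week (every 7 ± 2 days, unless otherwise stated"). The synopsis (Study Treatment) gives active drug "or placebo for 48 weeks in a randomized, double-blind design".

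The SAP does not define expected doses. It makes no exception for the first dose after a gap.

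The per-protocol set has its own dosing rules in SAP section 3. Relevant protocol deviation 7 applies to more than 2 doses, and the SAP says of it: "This addresses incorrect allocation of subject to active or control and missed doses". That rule does not refer to the compliance rate.

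**The concern.** The reference point for each dose is the injection actually given before it, not the scheduled date. A boy who misses one week and resumes on his usual day has a 14-day gap. The missed dose is absent from the numerator, and the correctly timed next dose is rejected as well. The denominator does not change, so one lapse costs two doses.

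Most readers will take an 80% compliance cut to mean that about four-fifths of doses were given. Under this rule the label also depends on how the misses are spread. Two boys with the same number of injections can receive opposite labels. What is at stake is the meaning of the one tabulated compliance figure in SAP 4.7.1; the rest of that section gives duration of exposure and per-subject listings.

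**Working it through.** The plan states no worked compliance figure, so there is nothing to reproduce. The check applies the rule to dosing dates.

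**Inputs.** Weekly dosing, an accepted gap of 5-9 days and a pass mark of 80% come from the SAP and Protocol Table 2-2. The number of expected doses, E, is an assumption: 48 weekly doses in 48 weeks, or 49 if a dose at the Week 48 visit is counted. The first dose is always given, all doses not named below are on schedule, and E is not reduced for misses.

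**Formula.** Let m be the number of missed doses and r the number of separate runs of misses that are followed by a later dose. Each such run also disqualifies the first dose after it. So

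- doses taken = (E − m)/E
- rate under the SAP rule = (E − m − r)/E

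**Pass mark.** For E = 48, 0.80 × 48 = 38.4, so 39 qualifying doses are needed.

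| Pattern of misses | Cost | Five missed (43/48 = 89.6% taken) | Most misses that still pass |
|---|---|---|---|
| Isolated, each followed by an on-schedule dose | 2 per miss | 38/48 = 79.2%, non-compliant | 4: 44/48 = 91.7% taken, scored 40/48 = 83.3% |
| One block of k, then back on schedule | k + 1 | 42/48 = 87.5%, compliant | 8: 40/48 = 83.3% taken, scored 39/48 = 81.3% |
| All at the end | 1 per miss | 43/48 = 89.6%, compliant | 9: 39/48 = 81.3% taken and scored |

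One more miss fails in each row: 5 isolated, 9 in a block and 10 at the end each give 38/48 = 79.2%.

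**E = 49.** The pass mark is 40 doses (0.80 × 49 = 39.2). Five isolated misses give 44/49 = 89.8% taken and 39/49 = 79.6% scored, so non-compliant. Five in a block score 43/49 = 87.8% and pass. The limits of 4, 8 and 9 are unchanged.

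**How often five misses fail.** With m = 5 and E = 48, failure needs r = 5: all five misses separate and none at the very end. If the misses fall at random among doses 2 to 48, the probability is C(42,5)/C(47,5) = 0.555. With four misses it is zero, because 48 − 8 = 40 still passes. With six (42/48 = 87.5% taken) it is about 98% by simulation.

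**Late doses.** A dose given 10 days after the last, followed by a return to the usual day, produces gaps of 10 and 4 days. Both fall outside 5-9. Five such episodes lose 10 doses: 38/48 = 79.2%, with 48/48 = 100% of doses taken.

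**Comparison.** With doses administered divided by doses expected, five misses give 89.6% whatever the pattern. A boy falls below 80% only at 10 misses (38/48 = 79.2%).

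**The case against.** The strongest reply is that the rule does not claim to measure the share of doses taken. It measures doses taken on time, and its window is the protocol's own 7 ± 2 days. A dose given 14 days after the last is off that interval, so rejecting it could be deliberate. It stands that timing is worth reporting and that the window is the right one.

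As a defence of the rule it falls short. The denominator is expected doses, so a miss is already charged there. Rejecting the next on-schedule dose charges it again. The result also ranks badly as a timing measure: of two boys who each missed five doses, the one who missed five weeks running is labelled compliant and the one with five single lapses is not.

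A second objection is about size, and it largely stands. A reader might infer that every missed dose counts twice, or that the 80% cut is in effect a cut near 92% of doses taken. The documents do not support either reading. A run of k misses costs k + 1, misses with no later dose cost one each, and the 92% figure applies only when every miss is isolated. The documents give no distribution of missed doses, so the shift in the reported percentage of compliant boys cannot be estimated. With four or fewer misses and other doses on time, nobody is reclassified.

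**Conclusion.** The point holds in a limited form. The rule double-counts an isolated miss followed by an on-schedule dose, and it does the same to a late dose followed by a return to schedule. When the remaining doses are on schedule, the score can equal or fall below the proportion of doses taken but never exceed it. The 80% cut becomes a pattern-dependent limit, running from 4 misses (91.7% taken) to 9 (81.3% taken).

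This rests on 48 or 49 expected doses, other doses exactly on schedule, and expected doses not reduced for misses. The 55% figure also assumes randomly placed misses and is illustrative.

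A reader might go further and infer that the table would mislead anyone asking whether a null result reflects under-dosing, or that analysis sets are affected. The documents do not support this. The table is descriptive and sits under the safety analyses. The primary analysis uses the mITT population (SAP 4.1.3 and 4.4.1), and the per-protocol set uses the relevant protocol deviations (SAP sections 3 and 4.1.4). Under-dosing can also be examined through the exposure summary and drug administration listings (SAP 4.7.1), the eight predose PK samples in the double-blind phase (Protocol Table 9.4-1) and the change in free myostatin (SAP 2.2.3). This is a minor correction that is worth making.

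**What to change.** In SAP 4.7.1.1:

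1. Define expected doses, stating whether a Week 48 dose counts and how early discontinuation changes the number.
2. Define the compliance rate as doses administered divided by doses expected, keeping the 80% to 110% limits.
3. Report intervals outside 5-9 days as a separate count, so that timing is shown without being mixed into the rate.

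The cost is SAP wording and table programming. The dosing diary already records the date of each home injection, clinic doses are recorded at source (Protocol 7.5), and accountability is checked at each visit (Protocol 7.6). No new data or protocol amendment is needed.
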